9.2.2 Patient-Reported Outcomes

9.2.2.1 Primary Endpoint

- Change in FACT/GOG-Ntx TOI score calculated as the difference after completion of 12 cycles of study therapy from baseline
- Change in FACT-MM TOI score calculated as the difference after completion of 24 cycles of study therapy from baseline

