9.3.4 Patient-Reported Outcomes (PRO) Endpoints

PRO compliance and completion rates will be tabulated at each collection time point and overall separately for the FACT-G (FWB and PWB subscales), FACT-Ntx, FACT-MM, ASK-12 and PRO-CTCAE instruments.

Health-Related Quality of Life (QOL)

To assess the impact of treatment and disease on health-related QOL, there are two co-primary endpoints: change in FACT/GOG-Ntx TOI from baseline to end of cycle 12 post-randomization (beginning of cycle 13 assessment) and change in FACT-MM TOI from baseline to end of cycle 24 (beginning of cycle 25 assessment) post randomization. The FACT-G (FWB and PWB subscales), Ntx and MM will be administered at the beginning (day 1) of every 3 cycles for the first 24 cycles (beginning of cycles 4, 7, 10, 13, 16, 19, 22 and 25) and every 6 cycles thereafter (up to completion of 48 cycles of therapy (beginning of cycles 31, 37, 43, and 49), or at treatment discontinuation prior to completion of 48 cycles of therapy. During long-term follow-up/post-treatment end, there will be four quarterly assessments for 1 year. We hypothesize that treatment with ixazomib will not result in a significant difference in the FACT/GOG-Ntx TOI over the first 12 cycles and that improved PFS will result in higher FACT-MM TOI scores by end of 24 cycles. All patients who receive at least one dose of study drug and complete the QOL assessment at both time points are eligible. Power calculations are based on t-tests comparing the two treatment arms for the change in score with a 2-sided 0.05 alpha split between these comparisons. In an unselected group of MM patients being treated with oral therapy (n=118), the FACT-MM TOI had a standard deviation (SD) of approximately 21 points. The FACT-Ntx TOI has a reported SD of 14-16.⁷⁰ We propose using a general effect size measure of half standard deviation to establish the minimally important difference (MID).^{47,69} We therefore will establish a MID of 10 for the FACT-MM TOI and 8 for the FACT-Ntx TOI. We assume 90% and 81% of patients are alive by year 1 and 2, respectively, as well as a 10% drop-out rate resulting in potential patients of n=414 and n=373 for each analysis. Sensitivity for the proportion assumed to submit the questionnaire at both time points (compliance rates of 60% and 80%), allowing for a range of instrument variability and assuming different correlation (0.6, 0.4) between repeated measures was performed (Table 3). The difference in the FACT-Ntx TOI mean change score over 12 cycles of treatment between the ixazomib-lenalidomide arm and the placebo-lenalidomide arm that can be detected with 80% power at 2-sided 0.025 significance level ranges from 3.7-6.9 points as shown below. The difference in the FACT-MM TOI mean change score over 24 cycles of

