There are two key secondary health-related QOL analysis comparing treatment arms: Time to worsening of the FACT/GOG-Ntx TOI and time to improvement of the FACT-MM TOI. Time to worsening of the FACT/GOG-Ntx TOI and time to improvement of the FACT-MM TOI will be analyzed with the KM method and compared using the log-rank test. We will establish significance as alpha=1.67% based on Bonferroni adjustment (5% divided over 3 comparisons). We will provide rates on each arm including exact binomial 95% confidence intervals for the FACT/GOG-Ntx TOI recovery rate and FACT-MM TOI response rate.

As exploratory, correlation between time to worsening of symptoms with PFS and OS will be assessed with Kendall's Tau adjusted for censored observations.

Finally, we will evaluate whether patients with poor treatment adherence based on medication calendars and lower likelihood of medication adherence based on ASK-12 scores have lower QOL scores [the FACT/GOG-Ntx TOI, FACT-MM TOI and FACT-G (FWB and PWB subscales)] after 12- and 24-cycles of treatment. Linear regression analysis at these 2 time points separately will be conducted with QOL score as outcome and treatment adherence group as the main effect adjusting for baseline QOL score along with other disease and demographic characteristics.

PRO-CTCAE

Analyses related to the PRO-CTCAE are exploratory. Descriptive statistics will be used to summarize selected PRO-CTCAEs tabulated at each cycle overall and by arm. We will map PRO-CTCAEs with provider reported AEs and evaluate differences in incidence and worst severity. PRO-CTCAE ratings will further be evaluated in relation to patient bother by treatment side effects (FACT-GP5 item, "I am bothered by treatment side effects") to identify the toxicities that are most highly associated with treatment tolerability issues.

Medication Adherence Scale

Analyses related to the ASK-12 are exploratory. Descriptive statistics will be used to summarize ASK-12 scores tabulated every 6 cycles on study therapy. The ASK-12 is reported to have a mean (standard deviation) of 27.5 (7.2). Differences between arms will be evaluated

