The difference in qPET parameters from the baseline ^{18}F -FDG PET/CT to the year 1 ^{18}F -FDG PET/CT will be reported by study arm. An analysis of covariance (ANCOVA) model will be used to test for a treatment effect on each qPET parameter, where the baseline qPET parameter value and an indicator for study arm are included as covariates, with the qPET parameter at year 1 as the model outcome.⁵⁹⁻⁶¹ Sensitivity of the findings will be examined by additionally adjusting the ANCOVA model for the randomization stratification factors (, as this would be expected to further improve precision of the study arm comparison.⁶²

In addition, longitudinal profiles of each qPET parameter from the baseline ^{18}F -FDG PET/CT through the year 2 ^{18}F -FDG PET/CT will be compared across study arm through an appropriately constructed linear mixed model.⁶³

Assuming that up to 15% of patients may not have either the baseline ^{18}F -FDG PET/CT scan performed or the year 1 ^{18}F -FDG PET/CT scan performed, or may have one or more of these scans uninterpretable, the proposed sample size of 510 patients (434 evaluable, 217 per study arm) has power of 80% using ANCOVA at a type I error rate of 0.05 to detect a difference in year 1 mean SUVmax between arms as low as 2.0, with only moderate correlation between the baseline and year 1 SUVmax ($R^2=0.45$) and common standard deviation as large as 10.0 (PASS 16). Larger correlation between baseline and year 1 SUVmax and/or smaller standard deviation of SUVmax would result in greater power.

13. Electronic Data Capture

Please refer to the EAA171 Forms Completion Guidelines for the forms submission schedule. Data collection will be performed in Medidata Rave and TRIAD.

Rev. Add1

Data for this study will be submitted via the Data Mapping Utility (DMU). Cumulative protocol- and patient-specific data will be submitted weekly to CTEP electronically via the DMU. DMU Light reporting consists of Patient Demographics, On/Off Treatment Status, Abbreviated Treatment and Course information, and Adverse Events as applicable. Instructions for setting up and submitting data via DMU are available on the CTEP Website: <https://ctep.cancer.gov/protocolDevelopment/dmu.htm>.

NOTE: All adverse events (both routine and serious) that meet the protocol mandatory reporting requirements must be reported via DMU in addition to expedited reporting of serious adverse events via CTEP-AERS.

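### The only test named for the two PRO co-primary endpoints is an unadjusted t-test on change from baseline; naming a baseline-adjusted analysis would cut the variance by 20–30% on the plan's own correlations

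*Combined protocol and SAP*

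**What the plan says.** Section 9.2.2.1 defines both PRO primary endpoints as differences from baseline. The first reads "Change in FACT/GOG-Ntx TOI score calculated as the difference after completion of 12 cycles of study therapy from baseline"; the second is the corresponding FACT-MM TOI change after 24 cycles. Section 9.3.4 calls them co-primary ("there are two co-primary endpoints: change in FACT/GOG-Ntx TOI from baseline to end of cycle 12 post-randomization", with the FACT-MM TOI change to the end of cycle 24 as the other).

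On testing, Section 9.3.4 says "Power calculations are based on t-tests comparing the two treatment arms for the change in score", "with a 2-sided 0.05 alpha split between these comparisons". Each comparison therefore has two-sided alpha 0.025. Table 3 gives detectable differences computed from the SD of the change score. For FACT-Ntx TOI, the text gives the difference "that can be detected with 80% power at 2-sided 0.025 significance level ranges from 3.7-6.9 points as shown below"; for FACT-MM TOI the range is 5.8–10.0. The MIDs are 8 and 10 points. The analysis set is treated patients with the assessment at both time points.

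Section 9.3.4 also plans linear mixed models with treatment, time and their interaction, with or without further predictors. It does not call them primary and does not say whether baseline is a response or a covariate.

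Baseline adjustment does appear elsewhere. The exploratory adherence regression in 9.3.4 is fitted "adjusting for baseline QOL score along with other disease and demographic characteristics". For the imaging change aim, Section 12.1.3.2 states "An analysis of covariance (ANCOVA) model will be used to test for a treatment effect on each qPET parameter", with the baseline value as a covariate.

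**The concern.** A change score subtracts the baseline with the slope fixed at 1. With equal SDs, the slope that minimises variance is the correlation itself, here 0.4 to 0.6, so the plan's own assumptions imply over-correction. Table 3 shows it directly: at SD 16.0 and correlation 0.4, the SD of change is 17.5, larger than the SD of the score being analysed.

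Two consequences matter. FACT-MM TOI has no margin in the plan's least favourable scenario, where the detectable difference equals the MID of 10. For FACT-Ntx TOI the plan expects no significant difference over 12 cycles. A noisier comparison makes non-significance easier to reach, so a narrow interval is what gives that result meaning.

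The baseline score is already collected, and the plan uses ANCOVA for an analogous baseline-to-follow-up comparison in imaging. It gives no reason for treating the PRO co-primaries differently.

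**Working it through.** **Inputs (Section 9.3.4 and Table 3).** Correlation ρ = 0.6 or 0.4; SD 12, 14, 16 (Ntx TOI) and 18, 20, 22 (MM TOI); 124 or 164 per arm (Ntx) and 112 or 148 per arm (MM) at 60% and 80% compliance; power 80%; two-sided alpha 0.025; MID 8 (Ntx) and 10 (MM). Equal SDs at both visits, as Table 3 assumes.

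**Step 1: reproduce Table 3.** SD of change = SD × √(2(1−ρ)). The detectable difference is approximately (2.241 + 0.842) × SD of change × √(2/n).

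- Ntx, SD 16, ρ 0.4, n = 124: SD of change = 16 × √1.2 = 17.53. Difference ≈ 3.083 × 17.53 × √(2/124) = 6.86; with the noncentral t, 6.90 (stated 6.9).
- MM, SD 22, ρ 0.4, n = 112: SD of change = 22 × √1.2 = 24.10. Difference ≈ 3.083 × 24.10 × √(2/112) = 9.93; with the noncentral t, 9.99 (stated 10.0).

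All 12 SDs of change agree within 0.05 and all 24 detectable differences within 0.1 point. Table 3 is correct for the test it describes.

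**Step 2: variance under baseline adjustment.** ANCOVA residual SD = SD × √(1−ρ²). The variance ratio to the change score is (1−ρ²) / (2(1−ρ)) = (1+ρ)/2.

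| Variance, in units of SD² | ρ = 0.6 | ρ = 0.4 |
|---|---|---|
| Follow-up score alone | 1.00 | 1.00 |
| Change score, 2(1−ρ) | 0.80 | 1.20 |
| ANCOVA, 1−ρ² | 0.64 | 0.84 |
| ANCOVA / change score | 0.80 | 0.70 |

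A simulation of both estimators at 124 per arm gave ratios of 0.82 and 0.70.

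**Step 3: detectable differences at the planned numbers (noncentral t).**

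| Scenario | Change score | ANCOVA |
|---|---|---|
| Ntx, most favourable (SD 12, ρ 0.6, 164/arm) | 3.67 | 3.28 |
| Ntx, least favourable (SD 16, ρ 0.4, 124/arm) | 6.90 | 5.77 |
| MM, most favourable (SD 18, ρ 0.6, 148/arm) | 5.79 | 5.18 |
| MM, least favourable (SD 22, ρ 0.4, 112/arm) | 9.99 | 8.35 |

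**Step 4: power at the MID, least favourable scenarios.** MM at 10 points: 80.1% with the change score, 92.6% with ANCOVA. Ntx at 8 points: 90.9% and 97.9%.

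**Step 5: precision for the Ntx comparison.** The half-width of a 97.5% interval in the least favourable Ntx scenario is about 2.241 × 17.53 × √(2/124) = 5.0 points for the change score. With ANCOVA (residual SD 16 × √0.84 = 14.66) it is 2.241 × 14.66 × √(2/124) = 4.2 points.

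**Step 6: do the mixed models recover this?** Only under some specifications. If baseline is one of the responses and the arms have free means at baseline, the complete-data treatment-by-time contrast equals the difference in mean change, so nothing is gained. The gain appears if baseline is a covariate or the arm means are constrained equal at baseline. Section 9.3.4 does not say which applies.

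**The case against.** The strongest reply is that little is lost. The sample size is set by overall survival, so no patients are recruited for the PRO test. Section 9.3.4 concludes that every scenario detects the MID or less, and the recalculation agrees. Only one of the 24 cells sits at its MID; the largest FACT-MM value at ρ 0.6 is 8.2 against an MID of 10. This stands, and it limits the point to an efficiency improvement.

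Several stronger readings are tempting but unsupported:

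- *That the plan prescribes the t-test as the confirmatory analysis.* The sentence describes the power calculation. The t-test as primary analysis is a fair inference because no other test is named for the co-primaries, but it is not stated. If the inference is wrong, the co-primary test is simply unspecified, and the same edit resolves it.
- *That the baseline is ignored.* It is subtracted. What is missing is an estimated slope.
- *That the change score is the least efficient standard option.* This holds at ρ 0.4 only. At ρ 0.6 it beats the follow-up score alone (0.80 against 1.00). ANCOVA beats both at either correlation.
- *That ANCOVA targets exactly the same quantity.* That needs equal expected baselines in the two arms. The analysis set is patients who complete both assessments, which is selected after randomization, so equality is not guaranteed. The methods paper cited for the imaging ANCOVA says in its title that ANCOVA has more power in randomized studies and also that it has more bias in nonrandomized ones. This does not favour the change score, but the two estimates need not coincide.
- *That using ANCOVA for imaging and not for PROs is a contradiction.* Different aims may use different methods. The imaging section shows only that the remedy is already familiar to this plan.

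**Conclusion.** The point holds as a gap in specification with a measurable efficiency cost. The analysis implied for the co-primaries has 1/0.80 = 1.25 to 1/0.70 = 1.43 times the variance of a baseline-adjusted one. Equivalently, ANCOVA would need 20% to 30% fewer analysed patients for the same precision (for example, about 99 or 87 per arm in place of 124). The practical gain is greatest for FACT-MM TOI at SD 22, ρ 0.4 and 60% compliance, which is close to the SD of about 21 that the plan cites.

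The figures rest on the plan's correlations and on equal SDs at the two visits; a higher true correlation would shrink the gain. Nothing here makes the change-score test invalid or leaves the PRO comparisons underpowered at the MID. The change is recommended rather than essential.

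**What to change.** In Section 9.3.4, name the co-primary PRO test explicitly: an ANCOVA with the follow-up TOI score (beginning of cycle 13 for Ntx, beginning of cycle 25 for MM) as outcome, and arm, baseline TOI score and the randomization stratification factors as covariates. A mixed model would serve equally if the text states that baseline is a covariate or that arm means are constrained equal at baseline. Test each at two-sided 0.025 and report the adjusted mean difference with its 97.5% confidence interval. State the role of any remaining mixed models.

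Either recompute Table 3 with SD × √(1−ρ²) in place of the SD of change, or keep it and label it conservative.

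The cost is SAP wording and, if chosen, a recalculated table. No new data, visits or patients are needed. ANCOVA will not correct selection from restricting the analysis to patients with both assessments; that still depends on the plan's sensitivity and missing-data analyses.

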
treatment between the ix-a lenalidomide arm and the placebo-lenalidomide arm that can be detected with 80% power at 2-sided 0.025 significance level ranges from 5.8-10.0 points. All of the scenarios show the target MID for each comparison or smaller can be detected with satisfactory power and thus we will be able to show a significant difference in QOL if it occurs.

Table 3

			Differences in FACT-Ntx TOI Subscale Mean Change Score (power=80%, 2-sided alpha=0.025)	
Standard Deviation (SD)	Correlation	SD of change	60% compliance (n=124/arm)	80% compliance (n=164/arm)
From Baseline to 12 Cycles Post Randomization				
12.0	0.6	10.7	4.2	3.7
	0.4	13.1	5.2	4.5
14.0	0.6	12.5	4.9	4.3
	0.4	15.3	6.0	5.3
16.0	0.6	14.3	5.6	4.9
	0.4	17.5	6.9	6.0
Differences in FACT-MM TOI Mean Change Score (power=80%, 2-sided alpha=0.025)				
Standard Deviation (SD)	Correlation	SD of change	60% compliance (n=112/arm)	80% compliance (n=148/arm)
From Baseline to 24 Cycles Post Randomization				
18.0	0.6	16.1	6.7	5.8
	0.4	19.7	8.2	7.1
20.0	0.6	17.9	7.4	6.4
	0.4	21.9	9.1	7.9
22.0	0.6	19.7	8.2	7.1
	0.4	24.1	10.0	8.7

Sensitivity analysis will be conducted to retain patients who discontinued treatment early and missing their FACT-Ntx TOI score after 12 cycles of treatment (beginning of cycle 13 assessment) using their QOL score at early treatment discontinuation for the analysis. For the FACT-MM TOI analysis after 24 cycles of treatment (beginning of cycle 25 assessment) the long-term follow-up assessment closest to 2 years from randomization will be used if patients are not on treatment. Descriptive statistics (mean, SD, median, range) will be used to evaluate the distribution of levels and

changes for the set of health-related QOL evaluations including the FACT/GOG-Ntx TOI, FACT-MM TOI and FACT-G (FWB and PWB subscales). Levels and changes will also be assessed graphically. Linear mixed effects models will be used to perform repeated measured regression analysis with the assumed covariance matrix maximizing Akaike information criteria. Models with treatment, assessment time, and treatment by assessment time interaction with and without other predictors will be fit. If there is substantial missingness, we will analyze the data according to the methods described in Schluchter and Schluchter, Greene and Beck. These methods consider missingness informative by jointly modeling longitudinal QOL score and survival time to dropout.

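### The two co-primary PRO tests are planned at a fixed 0.025 each; a Holm step-down would give equal or greater power at the same 5% family-wise error, an optional and modest gain

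*Combined protocol and SAP*

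**What the plan says.** Section 9.3.4 states that "there are two co-primary endpoints: change in FACT/GOG-Ntx TOI from baseline to end of cycle 12 post-randomization", the second being change in FACT-MM TOI to the end of cycle 24. Power rests on t-tests of the change scores "with a 2-sided 0.05 alpha split between these comparisons". For the Ntx TOI, the difference "that can be detected with 80% power at 2-sided 0.025 significance level ranges from 3.7-6.9 points as shown below"; for the MM TOI, the difference "that can be detected with 80% power at 2-sided 0.025 significance level ranges from 5.8-10.0 points". Table 3 uses the same level throughout.

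The expected results differ in kind. For neuropathy: "We hypothesize that treatment with ixazomib will not result in a significant difference in the FACT/GOG-Ntx TOI over the first 12 cycles". For disease control, the expectation is that "improved PFS will result in higher FACT-MM TOI scores by end of 24 cycles". On size: "We therefore will establish a MID of 10 for the FACT-MM TOI and 8 for the FACT-Ntx TOI".

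The split appears only as the basis of the power calculation. The section writes no separate decision rule for the two co-primary tests and no step-down or alpha-recycling rule. The key secondary PRO comparisons in the same section use a fixed Bonferroni level of 1.67%. No 97.5% confidence intervals are specified for the co-primaries.

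**The concern.** Under a fixed split, each co-primary is judged at 0.025 whatever the other shows. If one is rejected, the alpha assigned to it could pass to the other without breaching the overall 5%, and the fixed split leaves it unused. The plan expects the MM TOI to improve, so the endpoint most likely to be left at the stricter level is the Ntx TOI. That is where a real worsening would matter to patients: the first primary PRO objective (2.4.1.1) is to quantify how far ixazomib contributes to neuropathy. At stake is some power, mainly for differences smaller than the plan's own minimally important difference (MID).

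**Working it through.** **Inputs (9.3.4 and Table 3).** Overall two-sided alpha 0.05, so 0.025 per endpoint; 80% power. Ntx: SD 12-16, n = 124 or 164 per arm. MM: SD 18-22, n = 112 or 148 per arm. Within-patient correlation r = 0.6 or 0.4. MID 8 (Ntx) and 10 (MM). The correlation between the two test statistics is not given and is assumed below.

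**1. Reproduce Table 3.** SD of change = SD × √(2(1 − r)). Detectable difference = SD of change × √(2/n) × (2.241 + 0.842), where the bracket is 3.083.
- Ntx, smallest (SD 12, r 0.6, n 164): 10.73 × √(2/164) × 3.083 = 3.65; stated 3.7.
- Ntx, largest (SD 16, r 0.4, n 124): 17.53 × √(2/124) × 3.083 = 6.86; stated 6.9.
- MM, smallest (SD 18, r 0.6, n 148): 16.10 × √(2/148) × 3.083 = 5.77; stated 5.8.
- MM, largest (SD 22, r 0.4, n 112): 24.10 × √(2/112) × 3.083 = 9.93; stated 10.0.

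All 24 cells agree within 0.1 point.

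**2. Error control.** Fixed split: 0.025 + 0.025 = 0.05 (0.0494 if the tests are independent). Holm tests the smaller p-value at 0.025 and, only if that is significant, the other at 0.05.
- Both nulls true: an error needs at least one p-value at or below 0.025, so the probability is at most 0.05, exactly as for the fixed split. Simulation gives the same figure for both rules: 0.0495, 0.046 and 0.036 at correlations 0, 0.5 and 0.9.
- One null true: it can be rejected only if its p-value is at or below 0.05, so the probability is again at most 0.05.

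**3. Power when both endpoints have 80% power at 0.025.** Power at 0.05 is Φ(3.083 − 1.960) = 0.869. Under Holm, the power of one endpoint is P(its p ≤ 0.025) + P(its p lies between 0.025 and 0.05 and the other p ≤ 0.025).
- Independent tests: 0.80 + (0.869 − 0.80) × 0.80 = 0.855.
- Assumed correlation from −0.7 to 0.7, signed relative to the directions of the two effects: 0.868 down to 0.841, so about 84-87%.
- No MM effect, independent tests: 0.80 + 0.069 × 0.025 = 0.802, so Ntx gains almost nothing.

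**4. Detectable Ntx difference once MM is rejected.** Replace 3.083 by 1.960 + 0.842 = 2.802.
- Smallest: 10.73 × √(2/164) × 2.802 = 3.32.
- Largest: 17.53 × √(2/124) × 2.802 = 6.24.

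The range falls from 3.7-6.9 to about 3.3-6.2 points.

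**5. Ntx power at the MID of 8, MM already rejected.**
- Worst cell (SD 16, r 0.4, n 124): 8 / (17.53 × √(2/124)) = 3.594. At 0.025, Φ(3.594 − 2.241) = 0.912; at 0.05, Φ(3.594 − 1.960) = 0.949.
- Next largest gain (SD 14, r 0.4, n 124): 0.969 to 0.984. With the noncentral t the gain is about 1.6 points; every other cell gains less.

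**6. Cost on a null endpoint.** If MM is certain to succeed and Ntx is truly null, the Ntx-specific rejection rate is 0.050 under Holm against 0.025 under the fixed split.

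**The case against.** The strongest case for leaving the plan alone is that nothing in it is wrong. The split controls error, Table 3 reproduces, and every scenario there already detects the MID or less with at least 80% power. The headline gain of 4 to 7 points occurs at differences of 3.7-6.9, all below the Ntx MID of 8. All of this stands, and it makes the point optional.

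The plan's own hypothesis also cuts against a simple appeal to its expected scenario. If MM improves and Ntx is truly unchanged, there is no Ntx effect to find, and Holm only raises the chance of a false Ntx finding from 0.025 towards 0.05. That stands as a cost, though family-wise error stays within 5%.

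Independence is doubtful. Both TOIs contain the same 14 physical and functional well-being items (14 of 25 in the Ntx TOI, 14 of 28 in the MM TOI; section 6.3.1). Neuropathy that impairs those domains would also lower the MM score and make the MM rejection less likely. This is why the gain is given as a range, and why it vanishes when MM shows nothing.

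Finally, neuropathy detection does not depend on this test alone. The plan also has time to worsening of the Ntx TOI, PRO-CTCAE numbness and tingling, and clinician-graded toxicity comparisons. That lowers the stakes but does not favour the fixed split over Holm.

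**Conclusion.** The point holds as an optional efficiency gain. Holm never rejects less than the fixed split and keeps the same 5% family-wise error under any dependence. The gain is about 4 to 7 percentage points for an endpoint that sits at 80% power, provided the other endpoint also has 80% power and the correlation lies between −0.7 and 0.7. At the Ntx MID it is about 4 points in the worst cell and about 1.6 or less elsewhere. Holm is symmetric, so MM would equally be tested at 0.05 if Ntx were rejected first.

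A reader might infer that the fixed split is an error, or that it materially hides a neuropathy burden the protocol regards as important. The documents support neither: the split is valid, and Ntx power at the MID is already about 91% or more in every cell of Table 3. Nor would Holm help to show that ixazomib does no neuropathic harm. A less strict level makes worsening easier to detect; a non-significant result at either level does not demonstrate absence of harm, which would need a margin and a confidence interval.

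**What to change.** Before unblinding, add to 9.3.4 that the two co-primary PRO tests use the Holm procedure: the smaller p-value is tested at two-sided 0.025 and, if significant, the other at two-sided 0.05. State that the rule is applied once both p-values are available, since Ntx is measured at the start of cycle 13 and MM at the start of cycle 25. Keep Table 3 as the conservative first-step calculation. This also supplies the decision rule that the section does not now write out.

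Name two downsides in the same place. The endpoint-specific error for a truly null second endpoint can rise from 0.025 to at most 0.05. Any simple 97.5% confidence intervals reported are conservative and may include zero when the second step rejects; for example, an Ntx p-value of 0.04 after MM has succeeded would be significant under Holm although the 97.5% interval covers zero.

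The cost is a few sentences of text. It needs no new data, no additional patients and no change to Table 3.
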